### BMI

Subject's BMI will be derived in kg/m^2 in the clinical database

### Change From Baseline

Change from baseline is the arithmetic difference between post-baseline and baseline.

### End of Investigational Product Administration Date

End of IP administration for each subject is defined as the date the decision was made to end IP as recorded on the End of IP eCRF page.

### End-of-Study for Individual Subject

End of study for each subject is defined as the date the subject last completed a protocol-specified procedure. The date will be recorded on the End of Study eCRF page.

### Enrollment Date

Enrollment Date is defined in the date collected on the eCRF.

### Randomization Date

Randomization Date is defined as the date subject was allocated to a treatment group.

---

Investigational Product (IP)

The term 'investigational product' is used in reference to AMG 986 or placebo.

Last IP Dose Date

Last IP Dose Date for each subject is defined as the latest date IP is administered

Study Day

Post study day 1: study day = (date – date of Study Day 1) + 1

Pre study day 1: study day = (date – date of Study Day 1)

Study Day 1

Study day 1 is defined as the first day of administration of the investigational product after enrollment. The day prior to Study Day 1 is considered Study Day -1.

Treatment-Emergent Adverse Event (TEAE)

Events categorized as Adverse Events (AEs) starting on or after first dose of investigational product as determined by the flag indicating if the adverse event started prior to the first dose on the Events CRF and up to and including 30 days after the end of investigational product.

Serious Adverse Events

Serious adverse events (SAEs) are events categorized as AEs that are starting on or after first dose of investigational product as determined by the flag indicating if the adverse event started prior to the first dose on the Events CRF and up to and including 30 days after the end of investigational product.

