### 7.2.8 Physical Examination

The investigator or qualified designee will perform a physical examination at the time points indicated in [Section 7.1](#). Pre-dose abnormal findings will be reported on the medical history CRF. Any adverse change from the Baseline physical examination (Screening and Day -1 physical examination) will be documented on the Event CRF.

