#### **9.1.2 Adverse Events**

An adverse event is defined as any untoward medical occurrence in a clinical trial subject. The event does not necessarily have a causal relationship with study treatment. The investigator is responsible for ensuring that any adverse events observed by the investigator or reported by the subject are recorded in the subject's medical record.

The definition of adverse events includes worsening of a pre-existing medical condition. Worsening indicates that the pre-existing medical condition or underlying disease (eg, diabetes, migraine headaches, gout) has increased in severity, frequency, and/or duration more than would be expected and/or has an association with a significantly worse outcome than expected. A pre-existing condition that has not worsened more than anticipated (ie, more than usual fluctuation of disease) during the study, or involves an intervention such as elective cosmetic surgery or a medical procedure while on study, is not considered an adverse event.

If the severity of an adverse event changes from the date of onset to the date of resolution, record as a single event with the worst severity on the Event CRF.

The investigator's clinical judgment is used to determine whether a subject is to be removed from treatment due to an adverse event. In the event a subject, or subject's legally acceptable representative requests to withdraw from protocol-required therapies or the study due to an adverse event, refer to [Section 8.1](#) for additional instructions on the procedures recommended for safe withdrawal from protocol-required therapies or the study.

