### **9.1.3 Serious Adverse Events**

A serious adverse event is defined as an adverse event that meets at least 1 of the following serious criteria:

- fatal
- life threatening (places the subject at immediate risk of death)
- requires in patient hospitalization or prolongation of existing hospitalization
- results in persistent or significant disability/incapacity
- congenital anomaly/birth defect
- other medically important serious event

An adverse event would meet the criterion of "requires hospitalization", if the event necessitated an admission to a health care facility (eg, overnight stay).

Information for a serious adverse event is collected from signing of the ICF through 30 days post last dose of AMG 986 or placebo.

If an investigator considers an event to be clinically important, but it does not meet any of the serious criteria, the event could be classified as a serious adverse event under the criterion of "other medically important serious event". Examples of such events could include allergic bronchospasm, convulsions, blood dyscrasias, drug induced liver injury (DILI) (see [Appendix A](#) for DILI reporting criteria), or events that necessitate an emergency room visit, outpatient surgery, or urgent intervention.

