## 9.2.2 Adverse Events

### 9.2.2.1 Reporting Procedures for Adverse Events That do not Meet Serious Criteria

Adverse events possibly related to any study procedures/study-activity are reported from signing of the ICF. All other adverse events are reported from the time of randomization (first dose of investigational product). The investigator is responsible for ensuring that all adverse events observed by the investigator or reported by the subject that occur from signing of the ICF or from the time of randomization (after the first dose of IP) through the End of Study are reported using the Event CRF.

The investigator must assign the following adverse event attributes:

- Adverse event diagnosis or syndrome(s), if known (if not known, signs or symptoms),
- Dates of onset and resolution (if resolved),
- Severity [and/or toxicity per protocol],
- Assessment of relatedness to IP (AMG 986 or placebo),
- Assessments of relatedness to any study-mandated activity/procedure and
- Action taken

The adverse event grading scale used will be the Common Terminology Criteria for Adverse Events (CTCAE). The grading scale used in this study is described in [Appendix A](#).

The investigator must assess whether the adverse event is possibly related to the investigational product (AMG 986 or placebo). This relationship is indicated by a “yes” or “no” response to the question: Is there a reasonable possibility that the event may have been caused by the investigational product (AMG 986 or placebo)?

The investigator must assess whether the adverse event is possibly related to any study-mandated activity [eg, administration of investigational product, protocol-required therapies, use of medical device(s) and/or procedure (including any screening procedure(s))]. This relationship is indicated by a “yes” or “no” response to the question: “Is there a reasonable possibility that the event may have been caused by a study activity [eg, administration of investigational product, protocol-required therapies, use of medical device(s)], and/or procedure”?

The investigator is responsible for reviewing laboratory test results and determining whether an abnormal value in an individual study subject represents a clinically significant change from the subject’s baseline values. In general, abnormal laboratory findings without clinical significance (based on the Investigator’s judgment) are not to be

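### The SAP's treatment-emergent rule has no worsening limb, so a procedure-related AE or SAE recorded before first dose that worsens on treatment is left out of TEAE incidence, the first primary endpoint

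*SAP*

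**What the plan says.** SAP Section 6 (Treatment-Emergent Adverse Event) covers "Events categorized as Adverse Events (AEs) starting on or after first dose of investigational product as determined by the flag" that marks a start before the first dose on the Events CRF, up to and including 30 days after the end of investigational product. It has no limb for worsening. The SAE definition beside it applies the same start criterion: "Serious adverse events (SAEs) are events categorized as AEs that are starting on or after first dose of investigational product". The protocol does not define treatment-emergent, so the SAP wording is the operative rule.

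Protocol 9.1.2 contains two further rules. "The definition of adverse events includes worsening of a pre-existing medical condition". And when the severity of an event changes between onset and resolution, the site is to "record as a single event with the worst severity on the Event CRF".

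On what is recorded before dosing, Protocol 9.2.2.1 says "Adverse events possibly related to any study procedures/study-activity are reported from signing of the ICF"; all other non-serious events are reported only from randomization, which that section equates with first dose. For serious events, Protocol 9.1.3 says: "Information for a serious adverse event is collected from signing of the ICF through 30 days post last dose of AMG 986 or placebo". For the physical examination, Protocol 7.2.8 says: "Pre-dose abnormal findings will be reported on the medical history CRF".

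**The concern.** Each rule is reasonable by itself; the gap lies in how they combine. An event that opens before dosing at Grade 1 and reaches a higher grade on treatment is, under 9.1.2, still one record. That record keeps its pre-dose flag, and the SAP sorts on the flag alone, so deterioration during treatment is not counted as treatment-emergent.

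Whether the deterioration counts then depends on which CRF page held the pre-dose state. On the medical history page, worsening produces a new AE with onset after dosing. On the Event CRF, it does not.

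TEAE incidence is the first primary endpoint (Protocol 10.1.1.1; SAP 4.1.1). The SAP's SAE definition has the same gap: a non-serious procedure-related event opened before dosing that becomes serious on treatment falls outside it.

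**Working it through.** The plan states no figure on this point, so the check is to trace the rules and then see what one affected subject is worth.

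**Can a pre-dose AE record exist?** Yes. Procedure-related AEs and SAEs are collected from consent (Protocol 9.2.2.1 and 9.1.3). Protocol 10.1.2.1 also anticipates procedure-related AEs in subjects who withdraw before dosing.

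**Trace of the rules**

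| Step | Procedure-related AE or SAE opened before dosing | Same state held as medical history |
|---|---|---|
| Before first dose | Event CRF record, flagged as starting before first dose | Medical history CRF, no AE record |
| Worsens on or after first dose | Same record, worst severity entered (9.1.2) | Worsening is itself an AE (9.1.2), with onset after dosing |
| SAP Section 6 | Not a TEAE | TEAE |
| TEAE incidence | Not counted | Counted |

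**Does another section repair it?** No. SAP Appendix A only imputes partial or missing dates. SAP 10.5.1 tabulates the events that Section 6 has already selected.

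**Can it be recovered from the database alone?** Not from the flag and the grade. The single record holds only the worst severity, so a pre-dose-flagged event that was Grade 2 throughout looks the same as one that rose from Grade 1 to Grade 2 on treatment.

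**What one affected subject is worth.** If a subject has no other TEAE, the arm's incidence falls by 1/n. Planned arm sizes follow from Protocol 10.1.3 and 10.2:

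- Part A pooled AMG 986: 11 cohorts × 6 = 66; 1/66 = 1.5 points.
- Part A pooled placebo: 11 × 2 = 22; 1/22 = 4.5 points.
- Part B pooled AMG 986: 8 × 6 = 48; 1/48 = 2.1 points.
- Part B pooled placebo: 8 × 2 = 16; 1/16 = 6.3 points.
- Part C, per heart failure cohort: AMG 986 1/15 = 6.7 points; placebo 1/5 = 20 points.

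These are weights per subject, not estimates of how many subjects are affected. They use planned numbers. The SAP records early discontinuation, and in a smaller arm each subject would weigh more.

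**Direction.** The rule can only remove events from the count, so each arm's TEAE incidence is either right or too low.

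**The case against.** The strongest case against acting is that the gap is narrow and its effect uncertain.

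- **Reach.** A reader might infer that any AE begun before dosing is at risk. It is not. Only possibly procedure-related AEs and SAEs are recorded before dosing, and pre-existing conditions that worsen are still counted. This stands, and it makes the affected set small.
- **Certainty of the recording.** Protocol 9.1.2 does not say in terms that the original onset is kept, and the CRF-specific instructions mentioned in Protocol 12.3 are not among the documents. Some sites might open a new record for the worsening. That is fair, but the single-record rule speaks of change between the onset and resolution dates of one event, and its natural reading keeps one onset. If sites differ, the count also depends on the site.
- **Safety oversight.** A reader might infer that deterioration is hidden. It is not. Events of Grade 2 or higher go to the medical monitor within 24 hours for unblinded review (Protocol 6.2.1.3.1 and 9.2.2.1), and SAP 10.5.1 still presents every AE by subject. What is lost is a count in the incidence table.
- **Second primary endpoint.** Some worsening could appear as a clinically significant change in examination, vital signs, laboratory tests or ECG. This is a partial backstop at best: SAP 10.5.2, 10.5.3 and 10.5.5 plan mainly summaries over time, with no incidence table of such changes.
- **Bias between arms.** A reader might infer heavier loss on IV AMG 986, because Protocol 6.2.1 describes a pH 9.4 glycine solution against saline placebo. That describes the vial; Protocol 6.2.1.1 has the IV product prepared in normal saline bags. The documents give neither bag volume nor final pH, so they do not support this.
- **Part C dose steps.** A reader might also infer that an event starting at 10 mg and worsening at 100 mg is miscounted. It started after first dose, so it is a TEAE, and SAP 10.5.1 tabulates Part C by treatment group within each cohort, not by dose step. No planned table changes.

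**Conclusion.** The point holds within its narrow scope. SAP Section 6, applied with Protocol 9.1.2, leaves out of TEAE incidence any procedure-related AE or SAE that was recorded between consent and first dose and worsened on or after first dose. The SAP's SAE definition has the same gap. This is a stated rule that gives the wrong count, not merely a missing detail.

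The documents give no rate of pre-dose AEs and no count of those that worsened, so neither the number of subjects missed nor any imbalance between arms can be estimated. Any assumed percentage would also have to allow for affected subjects who have another TEAE and so stay in the incidence. What can be said is that the error is always an undercount, and that each subject lost is worth between 1.5 points (pooled Part A AMG 986) and 20 points (a Part C placebo arm) at planned numbers.

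The conclusion assumes that the single record keeps its original onset, and therefore its pre-dose flag, as 9.1.2 is most naturally read. The analysis is descriptive, with no hypothesis test at stake. The correction is still worth making, because this is the primary safety table and the repair is small.

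**What to change.** In SAP Section 6, define a TEAE as an AE that starts on or after first dose, or that started before first dose and increased in CTCAE grade or became serious on or after it. Leave the upper time limit unchanged, and align the SAE definition in the same way.

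Before database lock, query the records flagged as starting before first dose that are ongoing or end after first dose. Obtain the pre-dose grade from source, and count the events that worsened.

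The cost is one clause in the SAP, a few source queries, and a possibly slightly higher reported TEAE incidence. If the queries find no worsened event, the table does not change. Rewriting Protocol 9.1.2, or splitting records at the Part C dose steps, is not warranted now that the study has stopped early and the SAP serves an abbreviated report.

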#### **9.2.2.2 Reporting Procedures for Serious Adverse Events**

The investigator is responsible for ensuring that all serious adverse events observed by the investigator or reported by the subject that occur after signing of the informed consent through 30 days after the last day of the dosing interval of investigational product or end of study, whichever is later, are recorded in the subject's medical record and are submitted to Amgen. All serious adverse events must be submitted to Amgen within 24 hours following the investigator's knowledge of the event via the Serious Adverse Event Report Form (SAER). The SAER Form may also be utilized to report serious adverse events after the end of study (refer to [Section 9.2.2.3](#)).

See [Appendix B](#) for a sample of the Serious Adverse Event Report (SAER) Form.

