#### 10.5 Safety Analyses (Primary Endpoints)

##### 10.5.1 Adverse Events

The Medical Dictionary for Regulatory Activities (MedDRA) version 19 or later will be used to code all adverse events (AEs) to a system organ class and a preferred term. Subject incidence of all treatment-emergent AEs, serious AEs, AEs leading to withdrawal of investigational product, fatal AEs will be tabulated by system organ class and preferred term in descending order of frequency. All adverse event tables will be summarized **by pooled AMG 986 and pooled placebo treatment groups for part A and part B of the study and by each treatment group for each cohort HFrEF and HFpEF for part C of the study.**

Details of each adverse event will be presented and reviewed for each subject. Listings and/or narratives of any on-study deaths, serious and treatment-emergent adverse events, including early withdrawals due to adverse events, will also be provided should they occur.

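### SAP section 6 defines serious adverse events by onset timing alone, so read literally the SAE table would duplicate the TEAE table

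*SAP*

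**What the plan says.** SAP section 6 (Definitions) has consecutive entries for TEAEs and SAEs.

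- TEAE: "Events categorized as Adverse Events (AEs) starting on or after first dose of investigational product as determined by the flag", with the window running "up to and including 30 days after the end of investigational product".
- SAE: "Serious adverse events (SAEs) are events categorized as AEs that are starting on or after first dose of investigational product", followed by the same flag and the same window.

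Protocol section 9.1.3 defines the term differently: "A serious adverse event is defined as an adverse event that meets at least 1 of the following serious criteria". Six criteria follow, from death to other medically important events. The same section says "Information for a serious adverse event is collected from signing of the ICF through 30 days post last dose of AMG 986 or placebo". For reporting to the sponsor, protocol section 9.2.2.2 covers SAEs that "occur after signing of the informed consent through 30 days after the last day of the dosing interval of investigational product", or to the end of study if that is later.

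The SAP uses the category in section 10.5.1, under the heading for safety analyses of the primary endpoints: "Subject incidence of all treatment-emergent AEs, serious AEs, AEs leading to withdrawal of investigational product, fatal AEs will be tabulated". Protocol section 10.5.2.1.1 also plans an SAE table. SAP section 11, which lists changes from the protocol's analyses, does not mention the SAE definition.

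**The concern.** A definitions section exists so that a table can be produced and checked from the written rule. Here the rule omits the one property that makes an adverse event serious. A programmer or reviewer who followed section 6 would select every TEAE for the SAE table. The SAP would then carry two tables with different titles and the same content, and the SAE table would disagree with the protocol's definition.

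This table is one of the first that a reader of a first-in-human safety report looks for. This version of the SAP governs the abbreviated study report, in which several other safety outputs have been cut, such as subject-level vital-sign and ECG listings and the categorical QTcF summaries. The remaining adverse-event tables therefore carry more of the safety conclusion.

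**Working it through.** The plan states no figure for this point, so the check is a comparison of texts with one illustration.

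**1. Compare the two SAP definitions.** From the onset condition to the full stop, the TEAE and SAE entries are word for word the same, a run of 42 words. They differ only in the lead-in.

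**2. Look for a seriousness criterion.** After the term being defined, the SAE entry contains none of the stems *fatal, life, hospital, disab, congenital, medically, criteri, serious*. It has no cross-reference to protocol section 9.1.3.

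**3. Write out both rules.**

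| Rule | Seriousness required | Onset window |
|---|---|---|
| SAP TEAE | no | first dose to 30 days after end of product |
| SAP SAE | no | first dose to 30 days after end of product |
| Protocol 9.1.3 SAE | yes, at least 1 of 6 criteria | collected from consent to 30 days after last dose |

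The first two rows select the same events, so literally {SAE} = {TEAE}. Under the protocol, treatment-emergent SAEs are the subset of TEAEs that meet a criterion.

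**4. Illustrate the difference.** Protocol section 2.4.1 gives Part C data as of 01 June 2018: 12 heart failure subjects, 4 with a TEAE, none with a serious event.

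- Literal SAP rule: 4/12 = 33.3% of subjects with an SAE.
- Protocol rule: 0/12 = 0%.

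**5. Check the windows.** At the start, the SAP's SAE category excludes events between consent and first dose, although the Part A and Part B schedules mark SAE collection at screening and Day -1. At the end, the protocol's extension to end of study adds little. The end-of-study visit is Day 30, with a 1-day window where Table 15 gives one, so Day 31 at the latest. Thirty days after even a single Day 1 dose is also Day 31 (1 + 30).

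**The case against.** The best reply is that the SAP is not read alone. It says that it details analyses outlined in Protocol Amendment 8, and that protocol defines seriousness. SAP section 10.5.1 lists serious AEs separately from TEAEs, which makes sense only if the two sets differ. On that reading, the section 6 entry merely sets the time window for events already classified as serious. The interim summary in protocol section 2.4.1 supports this, because it already reports TEAEs and serious events as different counts. This stands as an account of what was probably intended and of what a programmer would probably do. It does not rescue the sentence, which is worded as a definition and gives a different set from the protocol's.

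Three stronger readings are tempting, and the documents do not support them.

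- *Pre-dose SAEs are lost.* They fall outside the SAP's SAE category and its table. However, section 10.5.1 also has the details of each adverse event presented by subject, and reporting to the sponsor under protocol section 9.2.2.2 is unaffected. Protocol sections 9.1.3 and 9.2.2.2 set collection and reporting windows, and a narrower tabulation window does not contradict them. A post-dose window is normal for a treatment-emergent SAE table; what is missing is that label.
- *SAE incidence will be reported as 33.3%.* The 4/12 figure assumes a program that ignores seriousness altogether. It shows what the words mean and does not predict the report.
- *A primary endpoint is affected.* The named primary endpoints are the incidence of TEAEs and of clinically significant changes in examinations, vital signs, laboratory tests and ECGs. SAE incidence is tabulated under the same heading but is not itself a named endpoint, and neither named endpoint changes.

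**Conclusion.** The point holds as a defect in the written rule. SAP section 6 defines SAEs only by timing, in the words used for TEAEs. Taken literally, this makes the SAE table in section 10.5.1 a copy of the TEAE table and conflicts with protocol section 9.1.3. The text comparison needs no assumption. Its size is illustrated by 4/12 against 0/12 in the interim Part C data, on the assumption that the sentence is applied exactly as written and seriousness is ignored.

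The practical risk is smaller than that contrast suggests, because the protocol's definition would probably be applied anyway. Protocol section 2.3 also reports no serious event in the programme up to 01 June 2018, so the documents show no event that the pre-dose gap had affected by that date. The correction should still be made, because the intended table cannot be derived from the SAP as it stands.

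**What to change.** Replace the SAE entry in SAP section 6 with:

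*An SAE is an AE meeting at least one seriousness criterion of protocol 9.1.3, as recorded in the study's SAE data (source field to be confirmed). A treatment-emergent SAE is an SAE that also meets the TEAE definition.*

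In section 10.5.1, label the table as treatment-emergent serious AEs, and add that any SAE with onset between consent and first dose is listed separately.

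The source field has to be confirmed because the documents do not show a seriousness flag on the Event CRF. The attributes listed in protocol section 9.2.2.1, which covers non-serious events, do not include one. The sample report form in Appendix B carries serious-criteria codes and refers to an SAE summary CRF.

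The cost is one replaced definition, one table title and one listing. No new data are needed, and no sample size or detection probability changes.
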